**Pilot Trial of the FMF Connect Teacher Companion Website**  
**Principal Investigators – [name] and [name]**

## **1. PURPOSE OF STUDY**

The purpose of this study is to evaluate feasibility of the FMF Connect Teacher Companion website and study design through a pilot trial. Specifically, we will investigate 1) intervention feasibility and 2) study design acceptability. Intervention feasibility includes technological feasibility of the website, acceptability of the website, and typical usage patterns. Study design acceptability includes enrollment and attrition rates, acceptability of randomization and control condition, assessment acceptability and sensitivity, optimal intervention length, and predictors of attrition.

Our hypotheses are:

- 1) the website will be technologically functional and acceptable to users, and users will show a moderate level of engagement with the website as evidenced by at least one hour per week of use.
- 2) the study design and assessments will be acceptable, the study will have sufficient enrollment to meet recruitment targets, and attrition will be predicted by teacher type (general education teacher) and teacher level of experience with FASD (teachers with less experience will be more likely to remain in the study).

This study is a pilot trial. Pilot trials are indicated when there is little information using a specific intervention technique in a certain population or the target population has been shown to need unique consideration of the topic (Bowen et al., 2009).

## **2. BACKGROUND AND RATIONALE**

Fetal alcohol spectrum disorders (FASD) affect an estimated 1.1-5% of children in the US (May et al., 2018) and can impact various aspects of neurodevelopment, including executive functioning, behavior, and academic performance. Although the majority of individuals with FASD are not intellectually disabled (Mattson et al., 2011), children with FASD perform lower than nonexposed individuals in academics (Crocker et al., 2015; Glass, 2016; Howell et al., 2006; Jirikowic et al., 2008). Without appropriate support, deficits in executive functioning and self-regulation may lead to difficulty organizing materials, planning, and sustaining attention as well as emotional and behavioral dysregulation. Teachers often lack understanding of FASD, leading to ineffective strategies and frustration. Lack of awareness and insufficient training on FASD in the school system creates significant barriers to services for children with FASD (Dybdahl & Ryan, 2009; Koren et al., 2010; Millar et al., 2017; Ryan & Ferguson, 2006; Ryan et al., 2006). Parents often report struggling to obtain services and supports for their children in schools and describe having to educate teachers and staff about FASD (Petrenko et al., 2014; Petrenko et al., 2020; Ryan & Ferguson, 2006; Ryan et al., 2006).

In-person trainings are limited in reach, while a digital intervention delivered via the internet can provide broader access and flexibility. The Families Moving Forward (FMF) Program is a scientifically-validated behavioral consultation program developed at Seattle Children's Research Institute/University of Washington by [name] and colleagues (Bertrand, 2009; Olson & Montague, 2011; Petrenko et al., 2017). It is usually delivered in person or via telehealth by trained specialists. It is designed for caregivers of

children with FASD and includes an in-person, targeted school consultation in which a specialist works with school staff to educate them on FASD, build a more positive home-school relationship, and discuss ways to better support the student. Educating teachers to increase their knowledge and awareness of FASD is hypothesized to help them to modify their attributions of the student's behavior and use more effective behavioral strategies, leading to improved self-efficacy and student-teacher relationship.

Given lack of widespread awareness of FASD, stigma, and numerous systems barriers (Petrenko et al., 2014; Roozen et al., 2020), many families in need of evidence-based intervention do not receive it. To address this need, the FMF Connect mobile Health (mHealth) app was derived from the standard FMF Program to directly provide caregivers with easily accessible, self-directed, evidence-based content and resources. In development and initial feasibility trials of FMF Connect, parents stressed the importance of materials or interventions for teachers (Petrenko et al., 2020; 2021). The FMF Connect Teacher Companion website was developed using the ADAPT-ITT framework (Wingood & Clemente, 2008) to address this need. It includes materials and exercises from the FMF Program and FMF Connect which have been adapted to teachers, incorporating a teacher needs assessment and a Teacher Advisory Board.

The current study will pilot the FMF Connect Teacher Companion website to determine technological acceptability and feasibility of study design and methods to inform a future RCT. This trial is designed using best practices in pilot/feasibility trials (Lancaster et al., 2004; Eldridge et al., 2016) and will follow the CONSORT extension for pilot trials in reporting and publishing (Eldridge et al., 2016). Aligning with the FMF model, the Teacher Companion website is the next logical step to disseminate this empirically-validated treatment and will complement FMF Connect in building a scalable and accessible network of support for children with FASD and their families.

The FMF Connect Teacher Companion website will increase accessibility of evidence-based materials on FASD for teachers, which is particularly critical for rural and other underserved populations. Websites can be easily accessed across a number of platforms including a mobile phone, tablet, laptop, or desktop computer, necessary for teachers who may work in a variety of settings, and are less likely to use a mobile phone in the classroom. This increased accessibility will allow teachers to more successfully manage behavior and support learning of students with FASD and will decrease barriers to quality care and services faced by many caregivers of children with FASD (Petrenko et al., 2014; Roozen et al., 2020; Ryan et al., 2006). This project will advance scientific knowledge relating to teacher awareness, perceptions, behavioral strategies, and self-efficacy related to FASD. It will also address a need for a systematically developed intervention which can be tested and improved through rigorous and reproducible research. Although some teacher resource websites for FASD exist, this will be the first empirically-derived and tested digital teacher intervention specific to FASD.

### **3. ADMINISTRATIVE ORGANIZATION**

This study is led by Drs. [name] and [name]. [name] is faculty at Mt. Hope Family Center and has appointments in the departments of Psychology and Pediatrics. [name] is faculty in the department of Electrical and Computer Engineering. They will oversee all research staff, implementation of human subjects' protections, and data collection, management, analysis, and reporting.

All data collection will be through our research team at the University of Rochester. Participants

will be recruited online and complete informed consent, screening, and survey through our REDCap database, hosted at the University of Rochester. Interview data will be collected via HIPAA-compliant Zoom. Additional data will be collected through the FMF Connect Teacher Companion website, developed and managed by our team and hosted on a URMC-managed Azure account.

#### **4. STUDY DESIGN**

The study design is a 2-parallel arm, staggered design pilot RCT. All subjects will complete baseline assessments. Then they will be randomly assigned to either Group 1) Website, or Group 2) Delayed treatment control. Group 1 will receive access to the website immediately. After six weeks, both groups will complete Timepoint 2 assessments. Selected participants will complete a qualitative interview about their experience using the website. After completion of Timepoint 2 assessments, Group 2 will receive access to the website (Group 1 will retain access to the website). After an additional six weeks, both groups will complete Timepoint 3 assessments and the study will conclude.

Assessments will include measures of FASD knowledge, teacher self-efficacy, teacher attributions and behavioral strategies, and satisfaction with the technology and study. Website usage data will be collected using Azure Application Insights (feature that can be enabled on our URMC-managed Azure account). Participants will be assigned to groups using simple randomization using manual 50/50 chance randomization.

#### **5. SUBJECT POPULATION**

The study population will be U.S. teachers of grades K-5. We will aim to enroll 90 participants to achieve a final sample size of 50, assuming a 45% attrition rate (consistent with recent 3-timepoint online studies in our lab). Additional participants will be enrolled if attrition is greater than anticipated.

#### **6. INCLUSION AND EXCLUSION CRITERIA**

Inclusion Criteria

Subjects must:

- Be an educational professional currently actively employed in a school setting in the United States
- Be above the age of 18 years old
- Have direct, consistent contact with a student with a diagnosed fetal alcohol spectrum disorder (FASD) or confirmed prenatal alcohol exposure (PAE) between the ages of 5-12, (i.e. grades K to 5) in a special or general education classroom
- Have reliable access to the Internet
- Be able to consent for themselves

Exclusion criteria:

Subjects will be excluded if:

- They are unable to read English
- They do not have direct, consistent contact with a student with a diagnosed FASD between ages 5-12 (e.g., substitute teacher, principal)

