## 7. RECRUITMENT METHODS

Subjects will be recruited nationally through a number of sources:

- In order to directly target teachers in under-resourced areas, we will identify low-income school districts using the Teacher Cancellation Low Income (TCLI) directory. This directory includes schools identified as low-income for the purposes of federal aid. We will randomly select districts in different states from this directory and reach out to administrative personnel about the study. If interested and willing, they will send out information about the study to the teachers in the district.
- We will also recruit via parent participants involved in trials of the FMF Connect app, all of whom have children with confirmed PAE or FASD. Parents with a child between the ages of 5-12 who have consented to receiving information about future research will receive an email informing them about the Teacher Companion website trial. This email will encourage them to share recruitment materials with their child's teacher for the upcoming year if interested. Teachers can then contact the study team if they would like to participate and will be encouraged to forward to any other eligible teachers.
- If these two methods do not prove adequate in recruiting sufficient and diverse subjects, we will target teachers and school staff through national email newsletters and social media forums specific to teachers. We will also send recruitment materials to disability- and FASD-specific networks such as the University Centers for Excellence in Developmental Disabilities (UCEDD) email listserv and FASD special interest groups. Finally, we will engage colleagues in the FASD field to send recruitment materials to their networks to recruit teachers who have a student with FASD.

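### The eligibility criteria do not exclude Teacher Advisory Board members, so people who helped shape the website could rate it, be interviewed about it and count toward its usage target

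*Combined protocol and SAP*

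**What the plan says.** Section 6 (Inclusion and Exclusion Criteria) has five inclusion and two exclusion criteria. The occupational criterion is "Be an educational professional currently actively employed in a school setting in the United States". The others concern age, contact with a qualifying student, internet access and capacity to consent. The exclusions are "They are unable to read English" and "They do not have direct, consistent contact with a student with a diagnosed FASD between ages 5-12 (e.g., substitute teacher, principal"). None refers to involvement in developing the website.

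Section 2 (Background and Rationale) describes that development. Of the website it says "It includes materials and exercises from the FMF Program and FMF Connect which have been adapted to teachers", and it describes the process as "incorporating a teacher needs assessment and a Teacher Advisory Board". It does not give the size of the board, what its members saw, or whether any teacher used the site before the trial.

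Four planned outputs depend on who the users are:

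- **Functionality and acceptability:** uMARS means and standard deviations plus interviews (section 17). Website crash reports also inform functionality.
- **Interviews:** five participants from Group 1 at Timepoint 2 and five from Group 2 at Timepoint 3, chosen by the team on usage, demographics and school setting (section 9).
- **Usage:** described in section 17, with at least one hour per week hypothesised in section 1.
- **Assessment sensitivity:** completion rates and pre-post effect sizes with 95% confidence intervals (section 17).

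Under section 15 (Subject Withdrawals), an enrolled participant is not removed without consent except under the fraud protocol.

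**The concern.** A pilot asks whether users who did not build a product find it workable. Someone who advised on its content is not an independent judge of it. Such a person may rate it more favourably, use it more, and give interview answers that reflect their own design choices. If allocated to delayed access, they may already know material that the arm is not supposed to have seen.

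Randomization does little to help. The uMARS is completed only by people who have had access. Usage and interviews are descriptive. The sensitivity measure is change within person. None of these is a contrast between randomized arms, so balance between arms does not remove the effect. Because removal after enrolment is restricted, the point has to be settled at screening.

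**Working it through.** **1. The plan's own figure.** Section 5 aims to enrol 90 for a final sample of 50 at 45% attrition. 50 / (1 − 0.45) = 90.9, or 91 rounded up; conversely 90 × 0.55 = 49.5. The stated figure reproduces to within one participant, and this point does not change it. The protocol gives no power calculation, effect size or standard deviation to check.

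**2. Can a board member enrol?** Set against section 6, a board member who works in a US school, is an adult, reads English, has internet access, can consent and has a qualifying student meets every inclusion criterion and neither exclusion. The gap follows from the text. How many such people exist does not.

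**3. Effect on the mean uMARS rating.** Assumption: 3 to 6 of 50 completers are board members, each rating 1 SD higher. Shift = share × 1 SD.

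- 3/50 = 0.06 SD; 6/50 = 0.12 SD.
- Half-width of a 95% interval for a mean at n = 50: t(0.975, 49)/√50 = 0.28 SD.
- At Timepoint 2 only Group 1 rates the site. With about 25 completers in that group, the half-width is t(0.975, 24)/√25 = 0.41 SD. If chance put all 3 to 6 in Group 1, the shift would be 3/25 = 0.12 to 6/25 = 0.24 SD.

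The shift stays inside the sampling uncertainty in each case. The interval would not, however, reveal that the shift was there.

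**4. Effect on the interviews.** One board member among five is 1/5 = 20%; two are 2/5 = 40%. If the five were independent draws at the assumed shares, the chance of at least one in a group would be 1 − (1 − f)^5:

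- f = 0.06: 1 − 0.94^5 = 0.27.
- f = 0.12: 1 − 0.88^5 = 0.47.

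Selection is purposive, so these figures only indicate scale. They show that a share too small to move a mean much can still reach an interview sample of five.

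**5. Effect on knowledge change.** Assumption: naive users gain 0.5 SD and a share f gains nothing. Mean gain = (1 − f) × 0.5.

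- f = 0.06: 0.47 SD.
- f = 0.12: 0.44 SD.

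The loss is proportional to f and small at these shares. If f is equal in the two arms, a between-arm difference shrinks by the same factor and does not change direction.

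**The case against.** The strongest reply is that the numbers are assumed and the effect is small. No count of board members is given, and the uMARS has no pass mark, so a shift of 0.06 to 0.12 SD changes no stated decision. The team chooses the interviewees and holds their contact details, so it could pass over people it recognises. Baseline knowledge is measured, so a ceiling would be partly visible. All of this stands, and it keeps the point minor. It does not close the gap: no rule tells the team to pass anyone over, and neither the uMARS nor the usage data has a baseline that would show familiarity.

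A reader might go further and infer that recruitment through FMF Connect families brings in teachers already trained through FMF. The plan does say "We will also recruit via parent participants involved in trials of the FMF Connect app", and the standard FMF Program "includes an in-person, targeted school consultation in which a specialist works with school staff to educate them on FASD". But section 2 describes FMF Connect as a self-directed app for caregivers; the school consultation is described for the specialist-delivered program. Parents are asked to "share recruitment materials with their child's teacher for the upcoming year if interested", who may be new to the family. The documents do not support the inference.

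Three other readings also go too far:

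- Needs-assessment respondents are not shown to have seen or shaped any content, so they should not be treated like board members.
- FASD networks and colleagues' contacts are a back-up, used only if the district and parent routes fall short.
- It cannot be said that nothing in the data identifies prior training. The Screening Form is cited but not shown, and section 1 makes experience with FASD a predictor of attrition, so some measure of it is implied.

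**Conclusion.** The point holds for Teacher Advisory Board members: section 6 admits them, and the outputs they would affect are not protected by randomization. It is a cheap improvement and does not threaten the trial. On the assumed shares, the effect on the uMARS mean is 0.06 to 0.12 SD and the knowledge gain falls by 6% to 12%, both small beside the sampling error at n = 50. The main gain is independence of the acceptability ratings and of two interview samples of five. This rests on two assumptions that the documents do not settle: that some board members have a qualifying student and would volunteer, and that board work made them familiar with the content. Prior FMF or FASD training among other teachers is not a defect of eligibility; the attrition hypothesis in section 1 needs variation in FASD experience.

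**What to change.** Add one exclusion to section 6: prior membership of the Teacher Advisory Board, or any prior access to the Teacher Companion website during development. The documents report no such access, so the second part is a precaution. Check both with one REDCap screening item before randomization.

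Optionally, if the Screening Form does not already do so, record needs-assessment participation and prior FMF or other formal FASD training. Keep those teachers eligible, and describe uMARS and knowledge change with and without them. With few such teachers, that table should be read as descriptive.

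The cost is one line of protocol text, one or two screening items and the loss of a few readily reached volunteers. The sample size and the rest of the design stay as they are.

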## 7. RECRUITMENT METHODS

Subjects will be recruited nationally through a number of sources:

- In order to directly target teachers in under-resourced areas, we will identify low-income school districts using the Teacher Cancellation Low Income (TCLI) directory. This directory includes schools identified as low-income for the purposes of federal aid. We will randomly select districts in different states from this directory and reach out to administrative personnel about the study. If interested and willing, they will send out information about the study to the teachers in the district.
- We will also recruit via parent participants involved in trials of the FMF Connect app, all of whom have children with confirmed PAE or FASD. Parents with a child between the ages of 5-12 who have consented to receiving information about future research will receive an email informing them about the Teacher Companion website trial. This email will encourage them to share recruitment materials with their child's teacher for the upcoming year if interested. Teachers can then contact the study team if they would like to participate and will be encouraged to forward to any other eligible teachers.
- If these two methods do not prove adequate in recruiting sufficient and diverse subjects, we will target teachers and school staff through national email newsletters and social media forums specific to teachers. We will also send recruitment materials to disability- and FASD-specific networks such as the University Centers for Excellence in Developmental Disabilities (UCEDD) email listserv and FASD special interest groups. Finally, we will engage colleagues in the FASD field to send recruitment materials to their networks to recruit teachers who have a student with FASD.

## 8. CONSENT PROCESS

Given this research is no greater than minimal risk and involves procedures for which written consent is normally not required outside of the research context (e.g., survey responses, website usage), we are requesting a waiver of documentation of consent. There is also not an easy way to verify participant identify for written eConsent without creating an additional step for participants involving communication with research staff through another method (e.g., email, phone).

Subjects who are interested in participating in the study will be directed to the REDCap Screening Module where they will view the Study Information Sheet. After reviewing the Study Information sheet, they will be asked several questions assessing their understanding of the information. All subjects will be given the option to download a copy of the Information Sheet for their records.

The study coordinator's contact information will also be presented if participants want to contact the coordinator with questions while reading the document. The study coordinator will document contact in the study contact log in REDCap. Additional items will screen for eligibility and obtain contact information.

The primary identifying information collected as part of this study are participant contact information in the REDCap Screening Module. This contact information would allow us to

contact participants in several anticipated scenarios, such as: if they indicate they have questions about the study, they provide inconsistent information we need to clarify, or to send them surveys or schedule interviews.

Identifying information will be stored separately from other de-identified data sources.

After reviewing the information sheet and completing comprehension questions, participants will be directed in REDCap to answer screening questions to assess eligibility for the study (see Screening Form). If eligibility criteria clearly aren't met (e.g., doesn't have a student with FASD), participants will be informed immediately that they aren't eligible and the module will end. Screening data will be maintained for ineligible participants to aid in clinical trial reporting requirements (e.g., documenting numbers screening, eligible vs. ineligible, and reasons).

This study is funded by the National Institute of Health (NIH). A Certificate of Confidentiality is automatically included as part of the notice of award. Language regarding the Certificate of Confidentiality is included in the consent documents.

Due to an increase in fraudulent participants across studies in our lab, we have developed a lab-wide guide to prevent, detect, and systematically manage fraudulent participants (see uploaded). For this study, if “red flags” (e.g., common email formula, unusual emails; see lab-wide guide for other examples) are identified by research staff, they will follow lab scripts to withdraw the participant.

